**Study design**

**Renal Transplant Recipients:**

All recipients will receive the same induction immunotherapy at time of transplant. : Campath (30mg IV x1) will be administered at the time of surgery. Methylprednisolone (500 mg IV) will be administered on the day of transplant and on days 1 (250 mg IV), and 2 (125 mg IV) post-transplant. No further steroids will be given post-transplant unless indicated by the following medical conditions: acute renal allograft rejection, renal diseases necessitating the use of steroids, and other systemic diseases such as rheumatoid arthritis (RA), systemic lupus erythematosus (SLE), and asthma.

Maintenance immunosuppression is administered according to the 1:1 randomization at time of enrollment: 20 subjects will begin **standard dose tacrolimus and MMF (control arm)**

Tacrolimus will be initiated according to our practice. The dose will be adjusted from day 3 on to achieve a target whole blood trough concentration of 8 ng/mL to 10 ng/mL. From month 2 until Month 6, the target tacrolimus trough level will be reduced to 6 ng/mL to 8 ng/mL. After month 6, the target level will be reduced to 4 ng/mL to 8 ng/mL.

MMF dose will be initiated as 1 g b.i.d. (2 g/day). Adjustments should be made for adverse events including but not limited to gastrointestinal intolerance and a decrease in WBC. MMF trough or AUC shall not be used to adjust dosing.

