### **Study purpose and rationale**

Immunosuppressive therapy with the calcineurin inhibitors (CNI) cyclosporine (CsA) and tacrolimus (Tac), has radically changed the field of organ transplantation. Ironically, although extensively and effectively used for kidney and other solid organ transplants, CsA and Tac cause significant adverse renal side effects: acute and chronic renal dysfunction, hemolytic-uremic syndrome, hypertension, electrolyte disturbances and tubular acidosis. Chronic nephrotoxicity from CNI has been implicated as a principal cause of post-transplant renal dysfunction. It is characterized by an irreversible and progressive tubular atrophy, interstitial fibrosis, and focal hyalinosis of small renal arteries and arterioles. Furthermore, by blocking IL2 production, this class of medications is also associated with a negative impact on generation of regulatory T cells, or (Tregs). (Tregs are an important subpopulation of helper T cells that has been associated with positive immunomodulation and donor specific hypo-responsiveness).

In renal transplant recipients, complete avoidance of calcineurin inhibitors from the time of renal transplant surgery has been associated with increased incidence of acute cellular rejection. The combination of mTOR inhibitors with full dose CNI has been shown to be synergistically nephrotoxic, and has been associated with poor graft outcome. We and other investigators have tested conversion from CNI to mTOR inhibitors with promising results. We have shown that in a prednisone-free immunosuppression regimen, conversion from tacrolimus to mTor inhibitors is safe, and not associated with an increased risk of acute rejection. More importantly, we have shown that it is associated with a persistent increase of regulatory T cells (Data presented at ATC 09 and 2010).

Recently, the A2309 study led to FDA-approval of Everolimus. The A2309 was a study designed to combine reduced dose CsA+Everolimus. Interestingly, the reduced exposure to CsA was not associated with an increased rate of ACR; renal allograft function was well maintained when compared to that of the control group. This study

---

study leads us to question the mechanism(s) behind the efficacy of a low dose CNI with an mTOR inhibitor in preventing acute allograft rejection.

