The present proposal is designed to investigate the mechanisms of the synergistic effect(s) of low dose CNI and mTOR inhibitors (Everolimus) in controlling alloreactive T and B cells while expanding Tregs.

Our hypothesis, based on published data and our laboratory results (see preliminary data-Supportive documents), is that mTOR inhibitors allow expansion of Tregs and that low exposure to CNI is sufficient to control alloreactive T cells. Decreased exposure to CNI and concomitant increase of Tregs will then translate to improved renal allograft function and histology.

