**Twenty (20) subjects will begin low dose tacrolimus with concentration controlled everolimus (treatment arm)**

Tacrolimus will be initiated according to our practice. In this treatment arm, the Tacrolimus dose will be adjusted from day 3 on, to a target whole blood trough concentration of 4 ng/mL to 7 ng/mL. From month 2 until Month 6, the target Tacrolimus trough level will be 3 ng/mL to 6 ng/mL. After month 6, the Tacrolimus dose should be adjusted in order to achieve a target trough level of 2 ng/mL to 5 ng/mL.

From day 5 on, the starting dose of Everolimus (0.75 mg bid) will be increased if the trough level is < 3 ng/mL, or reduced if the trough level is > 8 ng/mL.

All drugs will be administered in an open label fashion.

The following transplant recipient data will be collected at the time of randomization:.  
Demographics: Age at transplantation, sex and race.

Causes of end-stage renal disease

Transplant related information: donor age, histocompatibility and cross match data, viral serology, history of acute rejection and delayed graft function, use of ACEI and/or ARB, level of renal allograft function - estimated GFR ( e-GFR(12) using MDRD formula, proteinuria.

Blood samples will be obtained prior to randomization from all renal transplant recipients for baseline T and B cell functional activity and characterization of the cell subpopulations by flow cytometry.

-All recipients will be routinely followed at our Transplant center with post-transplant labs (SMA7, CBC, and relevant immunosuppression trough levels).

Additional blood will be collected and analyzed for the study at 3, 6, 12, 24 and 36 months post-randomization. If the final blood sample cannot be drawn at the 36 month timepoint, it may be drawn up to 50 months post-transplant. These samples will be used to investigate the impact of the two maintenance immunosuppressive regimens on subpopulation of T cells in comparison with baseline levels. Specifically,

---

we will look at regulatory T cells (Treg: Foxp3+CD4+ CD25bright+) that could have been generated via the two maintenance immunonousuppressive regimens, and correlate the generation of with their function.

RNA from peripheral blood will be also collected and stored for post-hoc analyses of T and B-cell immunoresponse gene expression via gene arrays.

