**Statistical analysis:**

The primary endpoints of the study are graft function and subpopulations of T cells, including regulatory T cells and B cell subpopulations at 3, 6, 12, 24 and 36 months post kidney transplant. The secondary endpoints of the study include 1) incidence of acute rejection, graft loss, and death at 12, 24 and 36 months post kidney transplant; 2) allograft immunohistopathology and gene expression profiles at 12 and 24 months post kidney transplant.

We will run univariate and bivariate analyses for all variables prior to our main analyses. We will evaluate continuous variables using t-tests or F-tests and categorical variables using  $\chi^2$ . We will examine data distributions and test all variables for linear relationships or non-linear relationships.

Descriptive statistics (means, standard deviation, frequency) and correlations (both Pearson and Spearman) among variables will be calculated for preliminary data assessment.

Necessary transformation and imputations will be carried out based on the raw data distribution.

As missing data are inevitable in a longitudinal study, we will determine whether missing data are MCAR (data are missing completely at random), MAR (data are missing at random), or NMAR (not missing at random). If missing data are MCAR or MAR, it is likely that the standard multivariate computations using PROC MI (multiple imputations) will not result in biased standard error estimates. However, if missing data are NMAR, we will use the "pattern mixture" approach to compute a weighted average of the parameters that are associated with the missing data to estimate what the data would have been.

For the primary objective, we hypothesize that subjects receiving low dose CNI with mTOR inhibitor (Everolimus) will exhibit significantly greater graft function and higher numbers of regulatory T cells as compared to the standard dose CNI+MMF group.

We will utilize both repeated-measures ANOVA and random mixed effect models to compare the trajectory change in graft function and proportion of regulatory T cells over 12, 24 and 36 months between the two experimental groups. The method of estimation will be maximum likelihood (ML).

---

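### The primary model names only months 12, 24 and 36, although months 3 and 6 are declared primary time points; all modelled visits fall where the tacrolimus targets partly overlap, and no by-arm trough summary is planned

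*Combined protocol and SAP*

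**What the plan says.** **Time points.** The opening of the Statistical analysis section lists five times for the primary endpoints: 3, 6, 12, 24 and 36 months. Study design schedules study blood at the same five times. The sentence that specifies the primary repeated-measures ANOVA and mixed models says they will "compare the trajectory change in graft function and proportion of regulatory T cells over 12, 24 and 36 months between the two experimental groups". Months 3 and 6 are not named there. Objectives lists months 12, 24 and 36 for graft function and unspecified time points for the cell subpopulations.

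**Tacrolimus targets.** In the control arm the early target is a "target whole blood trough concentration of 8 ng/mL to 10 ng/mL"; from month 2 to month 6 "the target tacrolimus trough level will be reduced to 6 ng/mL to 8 ng/mL"; and then "After month 6, the target level will be reduced to 4 ng/mL to 8 ng/mL". In the everolimus arm the dose is first adjusted "to a target whole blood trough concentration of 4 ng/mL to 7 ng/mL"; the target is 3 to 6 ng/mL from month 2 to month 6; and then "After month 6, the Tacrolimus dose should be adjusted in order to achieve a target trough level of 2 ng/mL to 5 ng/mL".

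**Use of troughs.** Study design includes immunosuppressant troughs in the routine laboratory follow-up of all recipients. The Statistical analysis section does not mention achieved troughs.

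**Rationale.** The study's hypothesis is that "Decreased exposure to CNI and concomitant increase of Tregs will then translate to improved renal allograft function and histology".

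**The concern.** There are two linked issues.

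First, the endpoint definition and the model sentence disagree about which visits count. If the model sentence is followed as written, data collected at two declared primary times are left out. Anyone who leaves before month 12 also drops out of the primary model, even with month 3 and month 6 values on file. Early losses need not be random: under Stopping Rules, recipients with certain infections are taken out of the study. Earlier outcomes are what a likelihood-based model would use to make a missing-at-random assumption more credible.

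Second, the visits that are named all lie in the one period when a recipient in either arm can be on target at the same trough. The arms are labelled by CNI exposure, and the rationale runs partly through lower exposure. Yet the plan never reports how far apart the arms actually were. From the planned analyses alone, a reader could not judge whether a small difference in graft function came with good or poor separation in tacrolimus.

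**Working it through.** **The plan's own figure.** Sample size and power states a power of 0.82 for an effect of 1.0 SD in graft function with 20 per arm, two-sided alpha 0.05 and 10% attrition.
- Per arm after attrition: 20 × 0.9 = 18.
- Noncentrality: 1.0 / √(1/18 + 1/18) = 3.0, with 34 degrees of freedom. Two-sample t-test power = 0.83. Without attrition (20 per arm) it is 0.87.
- For 2.0 SD (percent regulatory T cells), power at 18 per arm is above 0.99.

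The stated figures reproduce. They do not depend on the trough ranges.

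**Visits.**
- Declared: 3, 6, 12, 24, 36 (five). Named in the model: 12, 24, 36 (three). Left out: 2 of 5.
- With 40 recipients and no losses: 40 × 5 = 200 planned post-baseline values per endpoint, of which 40 × 2 = 80 are at months 3 and 6.
- Attrition of 10% by month 12: 40 × 0.10 = 4 recipients (2 per arm) with no outcome in a model restricted to months 12 to 36, although they may hold up to 4 × 2 = 8 earlier values.

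**Target ranges (ng/mL), from Study design.**

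| Period | Control | Everolimus arm | Midpoints | Midpoint difference | Control lower limit minus everolimus-arm upper limit |
|---|---|---|---|---|---|
| Day 3 to month 2 | 8–10 | 4–7 | 9.0, 5.5 | 3.5 | 8 − 7 = +1 |
| Months 2–6 | 6–8 | 3–6 | 7.0, 4.5 | 2.5 | 6 − 6 = 0 |
| After month 6 | 4–8 | 2–5 | 6.0, 3.5 | 2.5 | 4 − 5 = −1 |

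After month 6 the common band is 4 to 5. That is 1/4 of the control range (width 4) and 1/3 of the everolimus-arm range (width 3). The on-target difference, control minus everolimus arm, can run from 4 − 5 = −1 to 8 − 2 = +6.

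**How much overlap this implies.** The documents give no trough distribution. Assume, for illustration only, that troughs are uniform within range and independent between arms.
- Both members of a random pair lie in the common band: 1/4 × 1/3 = 1/12, about 8.3%.
- Control at or below everolimus arm: half of that, 1/24, about 4.2%.

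So the overlap is real but partial. Months 3 and 6 belong to the period when the ranges only touch, at 6 ng/mL, and the midpoint difference there is the same 2.5. Adding these visits recovers data but does not widen the target contrast.

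**The case against.** **The plan compares regimens.** The title, Objectives and primary hypothesis set tacrolimus plus everolimus against tacrolimus plus MMF. Everolimus versus MMF differs at every visit, whatever the tacrolimus troughs. This stands: the randomized comparison is intact. Even with no overlap, a difference between two-drug regimens could not be assigned to tacrolimus alone.

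**The ranges are not contradictory.** The range 2–5 lies below 4–8 at both limits. The control target does fall after month 6, from a midpoint of 7 to 6. The low range also matches the tacrolimus concentrations that the preliminary in-vitro work with sirolimus (Abstract ATC 2010) found most favorable. This stands too. A reader might infer that the labels standard and low are inconsistent with the ranges, but the documents do not show that.

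**The model sentence may mean follow-up horizons.** On that reading months 3 and 6 are included implicitly, and for graft function the named months match Objectives. The plan also mentions multiple imputation, which could draw on earlier visits. Both readings are possible, but neither is written down, and the endpoint definition in the same section gives five times for both endpoints.

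**Stronger inferences that the documents do not support.**
- That power collapses because the tacrolimus contrast may shrink. No passage links the 1.0 SD effect to a trough difference, and scaling it that way would credit everolimus with none of the effect.
- That an on-target everolimus recipient at 4–5 ng/mL falls under the warning "The combination of mTOR inhibitors with full dose CNI has been shown to be synergistically nephrotoxic". The documents never call that concentration full dose.
- That a null result should be declared inconclusive when separation falls below some threshold. That would condition a randomized comparison on a post-randomization measure, and nothing in the plan calls for it.

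**Conclusion.** The point holds in a limited form. The primary-model sentence leaves out two of the five time points that the same section declares primary. On the plan's own attrition assumption, read literally, it discards the outcomes of about 4 of 40 recipients. This is an inconsistency in specifying the primary analysis, and it holds whatever one thinks of the trough ranges.

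The exposure issue is secondary. All three modelled visits fall where the targets share a 1 ng/mL band, with midpoints 2.5 ng/mL apart, and no by-arm description of achieved troughs is planned. This weakens interpretation through the CNI-exposure mechanism in Study purpose and rationale. It does not invalidate the regimen comparison or change the stated power.

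The conclusion assumes that the model sentence is meant literally and that the 10% attrition figure applies to both arms. The pair percentages rest on the uniform-trough assumption and are illustrative.

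**What to change.** 1. In Statistical analysis, state that months 3, 6, 12, 24 and 36 all enter one likelihood-based mixed model for each primary endpoint, with treatment, visit and treatment-by-visit terms. Report the between-arm contrasts at months 12, 24 and 36 from that model. Use the same list of visits in Objectives.
2. As supporting description, report achieved tacrolimus troughs by arm and period: the mean difference with 95% CI, and the share of each arm at 4–5 ng/mL. The troughs are already measured in routine follow-up.

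No change to any trough target is proposed.

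**Cost.** No new visits or samples are needed, only wording and a little programming. With five visits an unstructured covariance has 5 × 6 / 2 = 15 parameters, against 3 × 4 / 2 = 6 with three. The visits are also no longer equally spaced, which bears on the first-order autoregressive and Toeplitz candidates in the plan. If achieved separation proves small, statements about CNI exposure will have to be more cautious.

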**Twenty (20) subjects will begin low dose tacrolimus with concentration controlled everolimus (treatment arm)**

Tacrolimus will be initiated according to our practice. In this treatment arm, the Tacrolimus dose will be adjusted from day 3 on, to a target whole blood trough concentration of 4 ng/mL to 7 ng/mL. From month 2 until Month 6, the target Tacrolimus trough level will be 3 ng/mL to 6 ng/mL. After month 6, the Tacrolimus dose should be adjusted in order to achieve a target trough level of 2 ng/mL to 5 ng/mL.

From day 5 on, the starting dose of Everolimus (0.75 mg bid) will be increased if the trough level is < 3 ng/mL, or reduced if the trough level is > 8 ng/mL.

All drugs will be administered in an open label fashion.

The following transplant recipient data will be collected at the time of randomization:.  
Demographics: Age at transplantation, sex and race.

Causes of end-stage renal disease

Transplant related information: donor age, histocompatibility and cross match data, viral serology, history of acute rejection and delayed graft function, use of ACEI and/or ARB, level of renal allograft function - estimated GFR ( e-GFR(12) using MDRD formula, proteinuria.

Blood samples will be obtained prior to randomization from all renal transplant recipients for baseline T and B cell functional activity and characterization of the cell subpopulations by flow cytometry.

-All recipients will be routinely followed at our Transplant center with post-transplant labs (SMA7, CBC, and relevant immunosuppression trough levels).

Additional blood will be collected and analyzed for the study at 3, 6, 12, 24 and 36 months post-randomization. If the final blood sample cannot be drawn at the 36 month timepoint, it may be drawn up to 50 months post-transplant. These samples will be used to investigate the impact of the two maintenance immunosuppressive regimens on subpopulation of T cells in comparison with baseline levels. Specifically,

---

we will look at regulatory T cells (Treg: Foxp3+CD4+ CD25bright+) that could have been generated via the two maintenance immunonousuppressive regimens, and correlate the generation of with their function.

RNA from peripheral blood will be also collected and stored for post-hoc analyses of T and B-cell immunoresponse gene expression via gene arrays.

Kidney biopsy samples will be collected with standard-of-care samples at time of transplant (back table), 3 months, 12 months and at 24 months post-transplant. These will help evaluateand compare the impacts of the two maintenance immunonousuppressive regimens on allograft immunohistopathology. Gene expression profiles will also be analyzed. These samples will be processed in the principal investigator's research laboratory.

Both groups of subjects will be followed through 36-months post-randomization. In addition to monitoring renal allograft function, we will evaluate the incidence of acute rejection, subject and graft survival, incidence of hypertension (HTN), malignancies, opportunistic infections and post-transplant diabetes mellitus (DM).

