### **Population**

The study will be conducted at Northwestern University Feinberg School of Medicine/Northwestern Memorial Hospital, and subjects will be recruited during visits to the Comprehensive Transplant Center. We plan to enroll and randomize recipients and their respective donors until 40 recipients have started the study drug to which they were randomized. As of January 2014, 3 recipients randomized to the experimental arm and 1 randomized to the control arm were withdrawn prior to dosing due to surgical complications. Replacement pairs will be enrolled, bringing the prospective enrollment to a minimum of 44 donor/recipient pairs (at least 88 total subjects).

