**Donors:**

Blood samples from donor subjects will also be obtained at either the time of randomization or post-surgery during standard-of-care follow-up appointments. These donor leukocytes will be used as stimulator cells in studies of functional activity of recipient T-cells. These samples will be processed in the principal investigator's research laboratory.

---

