A variety of covariance structures (first order regressive, compound symmetry, Toeplitz, variance components, unstructured) will be carefully examined and compared using the best fitting statistics, such as Akaike's Information (AIC) and Bayesian Information Criteria (BIC). These statistics are likelihood functions and can be compared across models. If, in spite of randomization, distributions of subjects' baseline characteristics are found to be different between the two experimental groups, these variables will be entered as covariates in the statistical analysis.

For the secondary endpoints, we will use logistic regression, Kaplan-Meier method, and Cox proportional hazards models to analyze time-to-event outcomes (acute rejection, graft failure, and death). For allograft immunohistopathology and gene expression profile outcomes, we will first develop a comprehensive immune profile of each participant by longitudinal analysis of frequency and function of T and B cell subsets. We will examine how these correlate with immunohistopathology and alloantibody production using Pearson or Spearman correlations. We will compare correlation coefficients between the two experimental groups using Z -tests to determine the distinct effects of each treatment arm. We will also compare the trajectory changes in cell populations and antibody production over 12, 24 and 36 months using both repeated measures ANOVA and random mixed effect models. All tests will be two-sided, and an error rate of  $\alpha < 0.05$  will be considered statistically significant. All data analyses will be performed using SAS 9.2 statistical software (SAS Inc., Cary, NC).

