### **Sample size and power**

[figure not shown]
We calculated our sample power for the two primary endpoints based on our clinical experience and small pilot data. Using a two-tailed  $\alpha$  of 0.05, the anticipated effect sizes corresponding to each specific aim between the two treatment arms were calculated using a minimum of 80% statistical power and assumed 10% attrition at 12 months.

For the sample size of  $n= 20$  in each group, the proposed study will have a power of 0.82 and 0.99 to detect effect size of 1.0 and 2.0 for graft function and % regulatory T cell change, respectively, between the two treatment arms. Because this is a pilot study, we do not consider the statistical power of secondary outcomes; It is anticipated that a much larger sample size will be needed in order to achieve statistical power for the secondary endpoints in this proposed study.

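### Graft function is a primary endpoint without a usable pre-treatment measure; donor pre-donation eGFR, available from enrolled living donors, should be recorded and prespecified as a covariate with donor age

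*Combined protocol and SAP*

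**What the plan says.** The Statistical analysis section states that "The primary endpoints of the study are graft function and subpopulations of T cells" (with B cell subsets), and hypothesizes better graft function in the everolimus arm. It plans repeated-measures ANOVA and mixed models to compare trajectories. Baseline characteristics become covariates only if their distributions are found to differ between arms.

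The Study design section, after the treatment-arm regimen, lists the recipient data collected at randomization. The transplant items begin "Transplant related information: donor age, histocompatibility and cross match data, viral serology". The same sentence continues with rejection history, delayed graft function, ACEI/ARB use, allograft eGFR by the MDRD formula, and proteinuria. Blood for baseline cell subsets is drawn before randomization.

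Randomization is 1:1 at enrollment (Study design). The Donors section treats randomization and post-surgery follow-up as alternative times for the donor blood draw. It gives one use for that blood: "These donor leukocytes will be used as stimulator cells in studies of functional activity of recipient T-cells".

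All grafts come from living donors (Inclusion Criteria), and donors are study subjects: replacement is described as "bringing the prospective enrollment to a minimum of 44 donor/recipient pairs (at least 88 total subjects" (Population).

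On power, the Sample size and power section says "the proposed study will have a power of 0.82 and 0.99 to detect effect size of 1.0 and 2.0". The first figure of each pair belongs to the kidney endpoint and the second to the Treg endpoint. The same section sets a "minimum of 80% statistical power and assumed 10% attrition at 12 months".

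**The concern.** The cell-subset endpoint has a pre-treatment value for each recipient. For graft function, the organ being measured is the donor's kidney, so the donor's kidney function before donation is the natural pre-treatment value, and one that the randomized regimen cannot have altered. It is not among the items listed. The one item that looks like a baseline, allograft eGFR at randomization, does not fit the plan's own timing.

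Two things are at stake. First, variation in recipient eGFR that came with the donor kidney stays in the error term when the arms are compared on level of graft function, the endpoint with the lower stated power. Second, with 20 per arm, a chance difference in donor kidney function would go unseen in the study data, and a rule that adjusts only for observed imbalances cannot act on a value that was not collected.

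**Working it through.** **1. Can the listed allograft eGFR serve as a baseline?** There are two readings.
- *Taken at randomization as described.* Randomization is at enrollment, and the Donors section sets it apart from post-surgery. The Population section reports randomized recipients withdrawn before dosing for surgical complications, which is consistent with randomization ahead of surgery. On this reading no graft is functioning in the recipient and the value cannot exist.
- *Taken early after transplant.* The same list holds delayed graft function and rejection history, so this may be what was meant. But tacrolimus targets differ between arms from day 3, so an early value may already carry a treatment effect, as well as the effect of surgery.

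Neither reading gives a value that is certain to precede treatment.

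**2. Reproducing the stated power.** Inputs from Statistical analysis and Sample size and power: two-sided α 0.05, effect 1.0 SD, 20 per arm, 10% attrition, so n = 20 × 0.9 = 18 per arm.

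Two-sample t-test: df = 2n − 2 = 34; noncentrality = d·√(n/2) = 1.0 × √9 = 3.0. Power = 0.830, against the stated 0.82. At d = 2.0 power exceeds 0.999, against 0.99. The stated figures therefore match an unadjusted comparison.

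**3. With donor eGFR and donor age as covariates.** R² is the share of recipient eGFR variance explained by the two together. It is **assumed**; the documents give no value.
- df = 2n − 2 − 2 = 32.
- Variance inflation for expected chance imbalance with k covariates: 1 + k/(2n − 3 − k) = 1 + 2/31 = 1.065.
- Noncentrality = d/√(1 − R²) × √(9/1.065) = 2.908 × d/√(1 − R²).

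| R² (assumed) | Noncentrality, d = 1.0 | Power, d = 1.0 | Power, d = 0.8 |
|---|---|---|---|
| unadjusted | 3.00 | 0.83 | 0.65 |
| 10% | 3.06 | 0.84 | 0.66 |
| 20% | 3.25 | 0.88 | 0.71 |
| 30% | 3.48 | 0.92 | 0.77 |

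**4. How much belongs to donor eGFR?** Donor age is already recorded, so the fair comparator is a model with donor age alone. If age carries half of each R² (a further assumption), then with one covariate (df = 33, inflation 1 + 1/32) power is 0.837, 0.856 and 0.875. The two-covariate powers are 0.844, 0.883 and 0.921. Donor eGFR then adds about 1, 3 and 5 percentage points.

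**5. Break-even.** For a single covariate, with the lost degree of freedom and expected imbalance charged, power returns to 0.83 at a correlation of about 0.17 to 0.18 (r² about 0.03). Below that there is no net gain.

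**6. Chance imbalance.** With 20 per arm the standard error of a difference in donor eGFR, in SD units, is √(2/20) = 0.316. A difference above 0.3 SD in either direction has z = 0.3/0.316 = 0.95, so it occurs in about 34% of randomizations.

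**The case against.** **A baseline is already listed.** A reader who stops at viral serology might infer that no graft-function value is planned at baseline. That is not what the document says: allograft eGFR is in the same sentence. What stands is narrower. By the plan's own timing, that item cannot be relied on as a pre-treatment value.

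**The main analysis compares trajectories.** A mixed model with subject intercepts already removes stable differences between kidneys from a comparison of change. This stands, and the power figures above do not apply to a pure slope comparison. They apply to comparing level, which the hypothesis of greater graft function leaves open.

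**Donor age is already recorded.** This also stands: part of the gain is available now. But the plan does not commit to using donor age unless the arms differ on it.

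**The gap cannot be fully verified.** The Evaluation schedule heading has no schedule beneath it in the available text, and the randomization list is headed as recipient data. A donor creatinine could appear in the part not shown, so the statement is limited to the readable text. The values are also unlikely to be lost, if they can be taken from donor charts; they are simply not in the planned dataset.

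**This is a pilot that meets its own target.** It does so at 1.0 SD without adjustment, and randomization protects validity. A reader might infer from this point that the stated power is wrong or the comparison biased; the documents support neither.

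**Conclusion.** The point holds as one of precision and of unclear baseline timing. The plan has no usable pre-treatment measure of graft function, the readable text records no donor kidney function, and no prognostic covariate is fixed in advance.

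With 18 per arm, a 1.0 SD effect and a comparison of level, adjustment for donor eGFR and donor age would move power from 0.83 to about 0.84, 0.88 or 0.92 at assumed R² of 10%, 20% or 30%. At the low end that is negligible. It would be too much to credit the whole gain to donor eGFR, since donor age supplies part of it. The gain matters more if the true effect is below 1.0 SD, where unadjusted power falls short of 80% (0.65 at 0.8 SD). The change is worth making because it is cheap, not because a stated figure fails.

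**What to change.** - Add to the randomization data list and the Donors section: the donor's last pre-donation serum creatinine, with donor age, sex and race, taken from the existing donor work-up. Compute donor eGFR by MDRD. Recover the values from charts for pairs already enrolled.
- State in the Statistical analysis section that donor pre-donation eGFR and donor age are covariates in the graft-function model whether or not they differ between arms.
- Reconcile the timing of the allograft eGFR item with randomization at enrollment: say when it is measured, and do not use it as a pre-treatment covariate if it is taken after the regimens diverge.

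Cost: abstraction of one routine laboratory value per donor, one CRF field for it, a sentence in the analysis section and two degrees of freedom. No new procedure is needed. If the covariates turn out to be weakly related to recipient eGFR, there is no net gain and a small loss of power is possible.
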